#### **7.11.3. EuroQoL 5 Dimensions 3 Levels (EQ-5D-3L)**

The EQ-5D Health Questionnaire is a self-completion standardized instrument for use as a measure of health outcome (<http://www.euroqol.org/about-eq-5d.html>). It consists of a descriptive system (EQ-5D) of health-related quality of life states, consisting of five dimensions (mobility, self-care, usual activities, pain/discomfort, anxiety/depression) each of which can take one of three responses. The responses record three levels of severity (no problems/some or moderate problems/extreme problems) within a particular ED-5D dimension. Additionally, the EQ-5D consists of a standard vertical 20cm visual analogue scale (EQ VAS) for recording an individual’s rating for their current health state (see [Clinical Outcomes Assessment manual](#)).

#### **7.11.4. Work Productivity and Activity Impairment Questionnaire adapted for Caregiving (WPAI:CG)**

The WPAI:CG is a self-reported measure of work productivity and impairment that yields four scores: Absenteeism (work time missed); Presenteeism (impairment at work/reduced on the job effectiveness); work productivity loss (overall work impairment/absenteeism plus presenteeism); and activity impairment. Each score is expressed as a percentage (0-100%) with higher numbers indicating greater impairment and less productivity ([Reilly et al, 1993](#); <http://www.reillyassociates.net/Index.html>; [Clinical Outcomes Assessment manual](#)).

Percent work time missed – a measure of absenteeism, calculated as work time missed due to health problem as a proportion of hours actually worked (Question 4).

Percent impairment while working – a measure of presenteeism, the degree to which health problem impacted work.

Percent overall work impairment – a measure of overall work productivity loss due to health problem, combining absenteeism plus presenteeism.

Percent activity impairment - a measure of the degree to which health problem has affected ability to do regular activities other than work at a job.

Each score is expressed as a percentage (0-100%) with higher scores indicating greater impairment and less productivity.

In this study, the WPAI:CG will measure the effect of a child/adolescent’s Duchenne muscular dystrophy on a caregiver’s work productivity and regular activities.

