### **Clinical Outcome Assessments (COA)**

- Change from baseline in the Pediatric Outcomes Data Collection Instrument (PODCI) Parent-report and Adolescent self-report scores.
- Change from baseline in the EuroQol 5 Dimensions 3 Levels (EQ-5D-3L) Health Questionnaire.
- Change from baseline in the EuroQol 5 Dimensions - Youth (EQ-5D-Y) Health Questionnaire.
- Change from baseline in the Healthcare Resource Utilization (HRU) questionnaire.
- Change from baseline in Zarit Burden Interview (ZBI).
- Change from baseline in the Work Productivity and Activity Impairment Questionnaire adapted for caregiving (WPAI:CG) in the percent work time missed, percent impairment while working, percent overall work impairment, and percent activity impairment due to a child's Duchenne muscular dystrophy.

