### **9. DATA ANALYSIS/STATISTICAL METHODS**

Due to the open-label design of the study, statistical analyses will be exploratory in nature. The data that will define the baseline for each analysis set will be outlined in the SAP.

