### **9.4. Exploratory Analyses**

#### **9.4.1. Clinical Outcome Assessments**

Summary statistics will be presented for the following endpoints by baseline, treatment and time point as applicable. Methodology for any treatment group comparisons will be specified in the SAP.

- Change from baseline in the PODCI Parent-report and Adolescent self-report scores.
- Change from Baseline in the EuroQol 5 Dimension 3 Levels (EQ-5D-3L) Health Questionnaire.
- Change from Baseline the EuroQoL 5 Dimensions – Youth.
- Change from Baseline in the Healthcare Resource Utilization (HRU) questionnaire.
- Change from Baseline in the Zarit Burden Interview (ZBI).
- Change from Baseline in the Work Productivity and Activity Impairment Questionnaire adapted for Caregiving (WPAI:CG) the percent work time missed, percent impairment while working, percent overall work impairment, and percent activity impairment due to a child's Duchenne muscular dystrophy.

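### WPAI:CG percent work time missed is defined with hours actually worked as the denominator, so it can exceed the 0–100% range that the same section states

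*Protocol*

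**What the plan says.** Section 7.11.4 of the protocol introduces four WPAI:CG scores and gives their common scale: "Each score is expressed as a percentage (0-100%) with higher numbers indicating greater impairment and less productivity". It then describes each score. Percent work time missed is "calculated as work time missed due to health problem as a proportion of hours actually worked (Question 4". Percent overall work impairment is "a measure of overall work productivity loss due to health problem, combining absenteeism plus presenteeism", with no combining formula. After the four descriptions the range is stated again: "Each score is expressed as a percentage (0-100%) with higher scores indicating greater impairment and less productivity".

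The section gives no cap on the absenteeism score and no rule for a week with zero hours worked. It does not say that the denominator also includes the missed hours. It refers to the Clinical Outcomes Assessment manual for the instrument.

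The score is a named endpoint. The Protocol Summary lists change from baseline "in the percent work time missed, percent impairment while working, percent overall work impairment" and activity impairment. Section 2.2.3.2 lists the same scores, and section 9.4.1 repeats them among the endpoints to be summarised. Section 9 states that "statistical analyses will be exploratory in nature".

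**The concern.** A ratio of hours missed to hours actually worked is not a percentage of work time. It compares two separate parts of the working week, so nothing holds it at or below 100%. The formula and the range stated on either side of it are incompatible.

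Three things follow if the sentence is programmed as it stands:

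- **Inflation that grows with absence.** The score is above the share of work time missed at any non-zero absence. The excess is non-linear, so it does not cancel in a change from baseline.
- **Loss of the most affected caregivers.** A caregiver who missed all work hours has a zero denominator and drops out of the summary. Those who missed nearly all contribute values of several hundred percent, which would dominate a mean and standard deviation.
- **Possible carry-over.** Percent overall work impairment is described as "combining absenteeism plus presenteeism", so a second named score could inherit the distortion.

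**Working it through.** **Inputs.** From section 7.11.4: the score is hours missed (M) over hours actually worked (W), and the stated range is 0–100%. The documents give no caregiver working hours, so the week lengths below are assumptions for illustration only.

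**Step 1: can the stated range be reproduced?** As written, the score is 100 × M/W. It is 0 when M = 0, equals 100% when M = W, exceeds 100% whenever M > W, has no upper limit, and is undefined at W = 0. The 0–100% range is not reproduced.

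**Step 2: which denominator fits the range?** With total work time M + W, the score is 100 × M/(M + W). This lies between 0 and 100% for any week in which there was work time to score.

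**Step 3: relation between the two.** Let s = M/(M + W). Then W/(M + W) = 1 − s, so M/W = s/(1 − s). This does not depend on the length of the week.

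| Share of work time missed, s | Score as written, s/(1 − s) |
|---|---|
| 10% | 0.10/0.90 = 11.1% |
| 20% | 0.20/0.80 = 25% |
| 50% | 0.50/0.50 = 100% |
| 60% | 0.60/0.40 = 150% |
| 75% | 0.75/0.25 = 300% |
| 90% | 0.90/0.10 = 900% |
| 100% | 1/0, undefined |

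**Step 4: the same absence in different assumed weeks (8 hours missed).**

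- 20-hour week: 8/12 = 66.7%, against 8/20 = 40%.
- 30-hour week: 8/22 = 36.4%, against 8/30 = 26.7%.
- 40-hour week: 8/32 = 25%, against 8/40 = 20%.

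**Step 5: effect on change from baseline (assumed 40-hour week).**

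- 4 to 8 hours missed: 8/32 − 4/36 = 25% − 11.1% = 13.9 points, against 20% − 10% = 10 points.
- 8 to 20 hours missed: 20/20 − 8/32 = 100% − 25% = 75 points, against 50% − 20% = 30 points.

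**Step 6: carry-over to overall work impairment.** The section gives no combining formula, so the size cannot be fixed. If absenteeism and presenteeism were simply added, with presenteeism assumed at 30%, then M = 24 and W = 16 would give 150% + 30% = 180%. With the corrected denominator the sum is 60% + 30% = 90%. A plain sum can still leave the range: at M = 30 and W = 10 it is 75% + 30% = 105%. The combining rule therefore needs its own check.

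**The case against.** The best reply is that section 7.11.4 describes a standard instrument and is not a programming specification. It points to the Clinical Outcomes Assessment manual, gives no formula for two of the other scores and no combining formula for the third, and never says that scores are to be computed from this prose. Derivations are usually left to the SAP or the instrument manual, and neither was available. The harm arises only if someone follows the sentence literally. This stands as a limit on the consequences. It does not remove the conflict, because the protocol does print a formula for this score. If the manual differs, the protocol disagrees with its own reference. If the manual agrees, the error is live.

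A second reply is that the text proves only a mismatch, and does not say which denominator was intended. When no more than half of the work time is missed, M/W stays within 0–100%, so the figures for low absence count as overstated only if M/(M + W) is accepted. That is correct: the strict contradiction lies above 50% absence and at zero hours worked, and how often caregivers fall there is unknown. Even so, M/(M + W) is the plain meaning of a percentage of work time missed, and it fits the stated range.

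Third, the corrected ratio is 0/0 for a caregiver with no hours worked and none missed. True, but that caregiver has no work time to score under either formula.

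**Conclusion.** The concern holds. Section 7.11.4 gives a formula that cannot produce the range the section states, and no other part of the protocol corrects it. Read literally, the score is s/(1 − s) in place of s. It breaches 100% once more than half of the work time is missed, and it is undefined when all of it is missed. These results need no assumption about week length. The worked examples in hours rest on assumed weeks. Calling values below the 50% point overstated rests on taking total work time as the intended denominator. Any effect on overall work impairment depends on a combining rule that the section does not give.

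The weight is low. This is one component of a caregiver questionnaire, among exploratory endpoints summarised descriptively in an open-label study. It touches no safety conclusion and no sample size, and the manual may already score it correctly. It is worth correcting because the protocol states a scoring rule for a named endpoint wrongly and the correction is nearly free.

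**What to change.** In section 7.11.4, state the denominator of percent work time missed as hours missed plus hours actually worked. Alternatively, delete the formula and say that all WPAI:CG scores are derived as set out in the Clinical Outcomes Assessment manual. Whichever is chosen, check the wording against the manual so that the two agree.

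Then confirm that percent overall work impairment is computed from the corrected absenteeism value, with a combining rule that keeps it within 0–100%. State that a caregiver with no hours worked and none missed has no absenteeism score.

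The cost is one sentence for the formula, plus a short check of the scoring. No new data collection is needed, because the same reported hours are used.

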### **7.11.5. Healthcare Resource Utilization (HRU) questionnaire**

The Healthcare Resource Use questionnaire is completed by the caregiver and asks questions about healthcare resources utilization related to their child's use of healthcare professionals, emergency room visits, and hospitalizations during the course of the study. Caregivers are also asked to estimate out-of-pocket costs related to healthcare resource utilization (see [Clinical Outcomes Assessment manual](#)).

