### **2.2.3.2. Clinical Outcome Assessments**

- To evaluate the long-term functional health effects of PF-06252616:
  - Changes from baseline in the Pediatric Outcomes Data Collection Instrument (PODCI) Parent-report and Adolescent self-report scores.
  - Change from baseline in the EuroQol 5 Dimensions 3 Levels (EQ-5D-3L) Health Questionnaire.
  - Change from baseline in the EuroQol 5 Dimensions - Youth (EQ-5D-Y) Health Questionnaire.
  - Change from baseline in Healthcare Resource Utilization (HRU) questionnaire.
  - Change from baseline in Zarit Burden Interview (ZBI).
  - Change from baseline in the Work Productivity and Activity Impairment. Questionnaire adapted for caregiving (WPAI:CG) in the percent work time missed, percent impairment while working, percent overall work impairment, and percent activity impairment due to a child's Duchenne muscular dystrophy.
  - Pooled or exploratory analyses, if conducted, utilizing the biobanked exploratory genomic and biomarker samples will be documented in the statistical analysis plan.

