It is important to note that some additional assessments may be required (eg, ambulatory status, PFTs to establish study baseline, medication history). As soon as these assessments are completed and a subject's eligibility has been confirmed, they may be enrolled into the study.

The PODCI child self-report (if eligible), EQ-5D-Y, EQ-5D-3L, ZBI, and HRU are new assessments not included in the parent study B5161002 and should be collected at screening and all subsequent visits outlined in the [Schedule of Activities](#). If a subject is unwilling to provide self-reported data they can still participate in the study.

If a subject becomes a screen failure for the current study, they will not be permitted to re-screen.

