- d. Determination of “yes” on the question of Actual Attempt, Interrupted Attempt, Aborted Attempt, or Preparatory Acts or Behavior for Suicidal Behavior section of C-SSRS.
- e. Acute suicidality to such a degree that precaution against suicide must be exercised.

At the time of withdrawal, procedures outlined in the early withdrawal visit should be performed as detailed in the [Schedule of Activities](#) and [Assessments](#).

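### HRU is not scheduled at Early Withdrawal, and its change-from-baseline endpoint has no stated look-back common to screening and follow-up

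*Protocol*

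**What the plan says.** Section 7.11.5 says the caregiver reports the child's use of healthcare professionals, "emergency room visits, and hospitalizations during the course of the study". On cost it adds, with a pointer to the Clinical Outcomes Assessment manual: "Caregivers are also asked to estimate out-of-pocket costs related to healthcare resource utilization (see". No other recall period is given in the protocol.

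The exploratory endpoint in Section 2.2.3.2 is "Change from baseline in Healthcare Resource Utilization (HRU) questionnaire". Section 9.4.1 plans summary statistics for the same quantity, and the Protocol Summary lists it too.

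Section 6 states that several questionnaires and "HRU are new assessments not included in the parent study B5161002 and should be collected at screening". Later collection follows the Schedule of Activities. The parent study therefore supplies no earlier HRU value.

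The Year 1 flowchart marks HRU at screening and Weeks 13, 25 and 49. The flowchart for Years 2, 3 and 4 marks it at two visits a year, read as Weeks 73/97, 121/145 and 169/193. In its Early Withdrawal column the HRU cell is empty. The caregiver PODCI, C-SSRS, EQ-5D-3L, ZBI and WPAI-CG are all marked there. Section 6.3 relies on that column: "At the time of withdrawal, procedures outlined in the early withdrawal visit should be performed as detailed in the" (the reference that follows is to the flowcharts and the assessment section).

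**The concern.** HRU counts events and costs over a period, so each value means something only together with the period it covers. The other caregiver questionnaires are collected at the withdrawal visit. HRU is not, so use between the last completed questionnaire and withdrawal is never asked about.

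This could affect many boys at once. Sections 3.2 and 6.3 allow subjects to be withdrawn if the parent study misses its objectives or stops early, or if the drug is commercialised.

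The second problem is the baseline. At screening essentially none of this study has elapsed, so a quantity defined over its course has nothing comparable to subtract. The protocol does name a time frame for other instruments: the C-SSRS refers to the period since the last visit (Section 7.2.7), and the EQ-5D-Y refers to the day of completion (Section 7.12.2). If the HRU look-back differs between screening and follow-up, or between follow-ups, an unscaled change mixes healthcare use with the length of recall.

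**Working it through.** The plan gives no HRU figure to reproduce. The check uses the Study Days in the two flowcharts.

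**1. Spacing.** HRU days after Day 1 are 85, 169, 337, 505, 673, 841, 1009, 1177 and 1345. Interval in weeks = (day − previous day)/7.
- Day 1 to Week 13: (85 − 1)/7 = 12
- Week 13 to 25: (169 − 85)/7 = 12
- Week 25 to 49: (337 − 169)/7 = 24
- Each of the six later intervals: 168/7 = 24
- Day 1 to Week 193: (1345 − 1)/7 = 192

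Screening can precede Day 1 by up to 42 days (6 weeks), so screening to Week 13 is up to 12 + 6 = 18 weeks.

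**2. Loss at withdrawal.** After Week 25, a boy who withdraws just before a scheduled HRU leaves almost 24 weeks uncovered. Between Weeks 13 and 25 the figure is almost 12 weeks. Before Week 13 he has a screening value and nothing after it. Assuming constant use of one contact per 12 weeks, the largest loss is 24/12 = 2 contacts. At assumed rates of 0.5 and 2 contacts per 12 weeks it is 1 and 4.

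**3. Change from baseline when use is constant.** Assume one contact per 12 weeks throughout, so the true change is zero. Expected count = window in weeks/12, and change = count at visit − count at screening.

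| Look-back assumed | Week 13 | Week 25 | Week 49 | Week 193 |
|---|---|---|---|---|
| Cumulative from Day 1, screening = 0 | +1 | +2 | +4 | +16 |
| Since last HRU, screening covers 12 weeks | 0 | 0 | +1 | +1 |
| Since last HRU, screening covers 24 weeks | −1 | −1 | 0 | 0 |
| One fixed window at every visit, or a rate | 0 | 0 | 0 | 0 |

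The +16 is 192/12. Rows two and three count the first interval from Day 1. With the full screening window, the Week 13 count would be up to 18/12 = 1.5 instead of 1. All entries scale with the assumed rate: at 0.5 or 2 contacts per 12 weeks the +16 becomes +8 or +32.

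The first three rows are illustrations that depend on a recall window the protocol does not state. The last row shows that unequal visit spacing does no harm by itself.

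**The case against.** The strongest reply is that Section 7.11.5 is a short description that points to a manual not available here. Its mention of the study's course may mean only that use is tracked throughout. Requiring HRU at screening suggests that the instrument has its own look-back. If that look-back is fixed and equal, the change is sound. The protocol also defers part of the matter: "The data that will define the baseline for each analysis set will be outlined in the SAP". Dividing counts by time is an ordinary SAP derivation, and nothing here prescribes raw counts.

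Most of this stands. A reader might infer that the endpoint cannot show whether healthcare use changed, or that a doubling or +16 would appear in the results. The documents do not support that. Those figures require a cumulative or since-last recall without time scaling. Even then, a 24-week screening window under since-last recall gives no rise above baseline.

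The reply does not reach the Early Withdrawal gap, because data never collected cannot be derived. Admissions are partly covered elsewhere, since adverse events are recorded through the last visit (Section 8.2) and inpatient admission makes an event serious (Section 8.6). But Section 8.7 lists admissions that are not in themselves serious events, and the adverse event provisions do not call for routine contacts or out-of-pocket costs.

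A reader might also infer that the gap biases use downwards. That is plausible if boys leave because of illness, but the protocol gives no withdrawal rates or reasons. A rate is biased only if use in the lost interval differs from use in the observed time.

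**Conclusion.** The Early Withdrawal gap holds: following the plan as written loses up to about 24 weeks of HRU data per withdrawing boy, and all post-baseline HRU for those who leave before Week 13. This assumes that the empty cell is also empty in the source table. The flowchart as read has a stray column, but the HRU row is exactly one mark short of EQ-5D-3L, ZBI and WPAI-CG, and its two marks line up with their first two. The weeks given for Years 2 to 4 rest on the same alignment.

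The baseline point holds conditionally. The protocol pairs a quantity described over the study's course with a change from screening, at unequal spacing, and states neither a common look-back nor a time scale. Whether the reported change would be distorted depends on the manual and the SAP.

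The consequence is small. HRU is one exploratory, descriptive questionnaire in an open-label extension, and no decision rule depends on it.

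**What to change.** 1. Mark HRU in the Early Withdrawal column, as for the other caregiver questionnaires. The cost is one more questionnaire at a visit already held.

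2. Align Sections 2.2.3.2, 7.11.5 and 9.4.1, with the matching line in the Protocol Summary, on one of two forms:
   - one fixed look-back of stated length, used at screening, every follow-up and Early Withdrawal; or
   - events and costs per unit of time covered, with the screening look-back stated so that it can be expressed as the same rate.

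   If the manual already fixes an equal look-back, stating it in Section 7.11.5 is enough. Asking about use since the last questionnaire should not be adopted without time scaling, because it would itself create the 12- and 24-week windows. The first form leaves uncovered any use that falls between windows. The second needs the dates of successive questionnaires.

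The cost of the second change is wording in the protocol and SAP, plus the questionnaire instructions if the recall period changes.

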### **7.12. Clinical Outcome Assessments (Subject completed)**

It is the intent to have all subject questionnaires completed electronically on a tablet or similar hand-held device for convenience of the patient and accurate data capture. However, if the license should in anyway prohibit use, an alternate delivery will be explored such as use of a paper version. If a suitable alternative is not found a questionnaire may be withdrawn from the protocol.

If a subject is unwilling to provide self-reported data, they can still participate in the study.

#### **7.12.1. Pediatric Outcomes Data Collection Instrument (PODCI)**

Children will become eligible to complete the Adolescent self-report version of the PODCI questionnaire once they are 11 years of age. The PODCI is a patient-reported assessment of musculoskeletal health intended for use in children and adolescents ([Daltroy et al, 1998](#); <http://www.aaos.org/>). The instrument contains 83 items and is organized into multiple domains: upper extremity function, transfers and mobility, physical function and sports, comfort (pain free), happiness and satisfaction, and expectations for treatment. Each domain produces an independent score, and a summary total score is also computed. These scores range from 0-100 with lower scores representing higher levels of disability. Scores may be reported as standardized, or they may be converted to normative scores based on the scores reported in a large, healthy population (see [Clinical Outcomes Assessment manual](#)).

